8.4. Source documents

The data will be recorded using a case report form (CRF) for each patient included. The CRF contains the queries and questionnaires required for all four indications; the indication-specific queries and questionnaires are to be completed for each indication and must be handed out to the patients. The completed original CRFs are the sole property of Pfizer and must not be provided to third parties in any format without the written approval of Pfizer, with the exception of authorized representatives of Pfizer or the appropriate competent authorities.

The treating physician is ultimately responsible for the collection and reporting of all clinical data, safety and laboratory data entered on the CRFs and other forms for data collection (source documents) and must guarantee that they are accurate, authentic/original, traceable, complete, consistent, legible, timely (contemporaneous), permanent, and available as required. The CRFs must be signed by the treating physician or authorized personnel. All corrections of entries on the CRFs and source documents must be dated, signed off, and explained (if required) and must not obscure the original entry.

In most cases, the source documents are patient records in the hospital or at the doctor's office. In these cases, the data collected on the CRFs must match the data in these records.

In some cases, the CRF or part of the CRF can also serve as a source document. In these cases, a document must be available at the doctor's study site and at Pfizer and must clearly identify the data recorded in the CRF and for which the CRF is considered a source document.

The clinical parameters recorded, especially those used to assess efficacy, are usual, known and recognized variables within each respective indication. All questionnaires used in the study have been validated.

8.5. Calculation of case numbers

It is assumed that the RA patients included in this study who are receiving a combined treatment (ETN + MTX) will be similar to those patients included in the randomized, double-blind DOSERA study in terms of the proportion of patients continuing treatment beyond week 12 (i.e. adequate efficacy - defined based on the DAS28 and the patient and physician global assessment of disease progression - has been attained). In that study, 22 - 26 % of the patients on combined treatment had attained no adequate efficacy after 12 weeks and continued treatment with etanercept (open-label), while conversely, adequate efficacy from treatment had been attained for 74 - 78 % of the patients at week 12. The sample size for this non-interventional study was calculated with the primary focus on the indication of RA.

Assuming that 74% of the patients under treatment with ETN + MTX and 66% of the patients under ETN monotherapy exhibit adequate response to treatment after 12 weeks (odds ratio of 0.682), 1200 patients (with a 2:1 ratio, this equals 800 patients under combined treatment and 400 patients under monotherapy) will be sufficient to detect a significant difference in the primary end point “proportion of patients attaining the desired treatment goal” with a power of 80% using a two-sided test with a significance level of 5%.

A logistic regression quoting the odds ratio and the corresponding 95% confidence interval is the appropriate statistical methodology for the analysis of this binary variable. As a sensitivity analysis, a GEE (generalized estimating equation) analysis can also be performed as a repeat method to obtain the binary response variable.

Because the combination with MTX is not recommended for the indications axSpA, PsO, and PsA, the inclusion of 300 patients in each of these indications appears sufficient for analysis of efficacy and tolerability.

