6.2. Study rationale

Approx. 20 - 30 % of patients end their treatment with etanercept during the first year of treatment, whereby the discontinuation of treatment is due to a lack of efficacy or side effects. The German and also the EULAR guidelines for the treatment of RA recommend a change of treatment after 3 and at most after 6 months if the criterion for low disease activity has not been attained [4, 11, 12]. The treatment guidelines for the other indications for which etanercept is approved are similar.

Clinical studies in the indications of RA, axSpA, PsA, and PsO show that it may be worth continuing treatment beyond a period of 12 weeks even if the criterion for low disease activity has not yet been attained, because the number of patients who only attain this criterion beyond the 12 weeks is increasing.

In routine care, according to national and EULAR guidelines, the medical assessment of the treating rheumatologist or dermatologist and other criteria should be taken into consideration in addition to the purely numerical assessment of treatment goals. Therefore, the assessment as to whether the treatment goals were ultimately attained depends in everyday clinical practice not only on the numerical results from the DAS, ASDAS (or PSARC) or PASI tools, but also on the overall evaluation of the physician and the patient, as well as on the treatment outcomes reported by the patient ("patient reported outcomes," PRO), treatment satisfaction, and other social and functional factors.

In summary, it is therefore the primary goal of this study to check how many patients in everyday clinical practice benefit from the continuation of treatment with etanercept beyond 12 weeks, even if the defined treatment goal has not yet formally been attained at that time but treatment is continued based on the judgment of the prescribing physician and the patient. In so doing, this rate is to be compared across the different indications. The variables which also reflect compliance with the treatment guidelines by physicians are to be examined in terms of additional influencing factors such as disease duration, concomitant medications, or PROs.

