8.1.2. Primary study end points

- Patients with RA: Proportion of patients who attain the desired treatment goals (see Table 2) at the week 12 and week 24 time points under monotherapy or in combination with MTX and maintain these long-term over a period of 52 weeks.
- Other indications: Proportion of patients who attain the desired treatment goals according to guidelines (see Table 2) in each respective indication at the week 12 and week 24 time points.

8.1.3. Secondary end points at weeks 12, 24, 36, and 52

All patients:

- Proportion of patients who continue treatment with etanercept,
- Occurrence of adverse events,
- Remission,
- Patient global assessment,
- Fatigue,
- Pain (VAS),
- Physician global assessment,
- PHQ-2
- Comparison of the parameters “patient global assessment,” “fatigue,” “pain,” “physician global assessment,” and “PHQ-2 across all indications,
- Comparison of FFbH and morning stiffness among patients with RA, axSpA, and PsA,
- Discontinuation of treatment due to a lack of efficacy or adverse events,
- Nature of further treatment if treatment has been discontinued,

Additionally for RA patients:

- FFbH
- CDAI
- SDAI

Additionally for axSpA patients:

- BASDAI,
- FFbH
- Enthesitis
- Occiput-to-wall distance

Additionally for PsA patients:

- BSA

- Dactylitis
- Enthesitis
- FFbH

Additionally for PsO patients:

- PASI, median time to PASI75, body segment (head, trunk, upper and lower extremities) and component-related subscales (erythema, induration, flaking) over 24 weeks,
- DLQI,
- Pruritus
- BSA.

The following indication-related laboratory tests will be documented if they are available as part of a routine assessment:

- Erythrocyte sedimentation rate (ESR), C-reactive protein (CRP)

In addition, the following laboratory tests will be documented for patients with RA, PsA, and axSpA if they are available as part of a routine assessment:

- Rheumatoid factor (RF) and anti-CCP antibodies.
- HLA-B27 at Visit 1 (just axSpA).

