8.2. Study setting

8.2.1. Study conduct

The planned recruitment period is 18 months. With a planned observation duration of 12 months per patient, the entire study would thus last for 30 months. The study is to start in Q1/2015 and will be ended in Q3/2017. In all, about 2100 patients in 300 centers are to be included in this non-interventional study, of whom about 1200 will have a diagnosis of RA and about 300 each will have a diagnosis of axSpA, PsA, and PsO.

After regular initiation on treatment with etanercept, patients will be documented for a period of up to 12 months. In accordance with section 67, paragraph 6 of the AMG, notice of the conduct of the study will be made to the National Association of Statutory Health Insurance Physicians, the Central Federal Association of Health Insurance Funds, and the competent central federal authority. Logistics, database creation, data input, and evaluation and reporting will be performed by a CRO Winicker Norimed.

Due to the high number of participating centers and patients throughout Germany, it is expected that the results from the study will have a representative nature. Another advantage of the study design lies in the fact that the 4 different indications will be examined within one study setting, which should improve the comparability of the study results across indications.

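### Section 8.5 claims 80% power from 1200 RA patients, but 1200 is also the planned enrolment and the 2:1 split is assumed, so the design does not ensure that power.

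*Combined protocol and SAP*

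**What the plan says.** Section 8.5 sizes the study on RA. Its response rates at week 12 are given as "Assuming that 74% of the patients under treatment with ETN + MTX and 66% of the patients under ETN monotherapy", with an "odds ratio of 0.682". It then states that "1200 patients (with a 2:1 ratio, this equals 800 patients under combined treatment and 400 patients under monotherapy) will be sufficient" to detect the difference "with a power of 80" per cent, "using a two-sided test with a significance level of 5" per cent.

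Section 8.2.1 describes recruitment of about 2100 patients, "of whom about 1200 will have a diagnosis of RA". Neither section adds an allowance for patients who cannot be analysed.

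Four other places bear on how many RA patients will be analysed, and in which group:

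- Section 8.9 anticipates premature withdrawals and says that their missing observations are usually not replaced.
- Section 8.1.3 has ESR and CRP recorded only "if they are available as part of a routine assessment", while the RA treatment goal in Table 2 is a DAS28 threshold.
- Section 8.2.2 requires the decision to start etanercept to be independent of the study. It sets no quota for MTX use and does not restrict RA patients to etanercept with MTX or etanercept alone.
- Section 8.7 analyses the primary end point by logistic regression for those two RA subgroups only.

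**The concern.** The calculated number and the enrolled number are the same. The split 800 + 400 already uses every RA patient, so each patient without a DAS28-based outcome, or on a regimen other than the two named, reduces the analysed number below the calculated one. The ratio matters as well. Power depends heavily on the smaller group, and in this design the treating physician's prescribing decides how large the monotherapy group is.

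This is the only power statement in the protocol, and it concerns the only comparison of the primary end point for which a model is named. If the contrast between combination and monotherapy is not significant, a reader may rely on the stated 80% to conclude that a difference of 8 points would probably have been found. That inference needs the evaluable number and the split to turn out as assumed.

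**Working it through.** **Inputs (section 8.5).** p1 = 0.66 (monotherapy), p2 = 0.74 (with MTX), d = 0.08, two-sided α = 0.05 (z = 1.960), power 0.80 (z = 0.842), ratio r = 2. Planned RA enrolment (section 8.2.1): about 1200.

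**Step 1: odds ratio.** (0.66/0.34) / (0.74/0.26) = 0.682, as stated.

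**Step 2: the plan's sample size.** The pooled proportion is p̄ = (0.66 + 2 × 0.74)/3 = 0.7133.

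Uncorrected: n1 = [1.960·√((1 + 1/r)·p̄(1 − p̄)) + 0.842·√(p1(1 − p1) + p2(1 − p2)/r)]² / d² = (1.0855 + 0.4765)² / 0.0064 = 381.2. Rounded up, this is 382 + 764 = 1146.

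Continuity-corrected: n1′ = (n1/4)·[1 + √(1 + 2(r + 1)/(n1·r·d))]² = (381.2/4)·[1 + √1.0984]² = 399.8. Rounded up, this is 400 + 800 = 1200, which is exactly the plan's figure.

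The reserve is therefore zero on the formula that reproduces the plan. On the uncorrected formula it is 1200 − 1146 = 54 patients (54/1200 = 4.5%).

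**Step 3: power at 800/400.** Power = Φ[(d − c − 1.960·s0)/s1], where

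- s0 = √(p̄(1 − p̄)(1/n1 + 1/n2)) = 0.02769
- s1 = √(p1(1 − p1)/n1 + p2(1 − p2)/n2) = 0.02831
- c = 0 (uncorrected) or ½(1/n1 + 1/n2) = 0.001875 (corrected)

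Uncorrected: Φ(0.909) = 81.8%. Corrected: Φ(0.842) = 80.0%.

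**Step 4: power under other evaluable numbers and splits.** The documents give neither a loss rate nor an expected split, so both are assumptions. Same formula; each cell is uncorrected / continuity-corrected, in per cent.

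| Evaluable RA patients | 1:1 | 2:1 | 3:1 | 4:1 |
|---|---|---|---|---|
| 1200 (no loss) | 86 / 84 | 82 / 80 | 75 / 73 | 69 / 66 |
| 1080 (10% loss) | 82 / 80 | 78 / 76 | 71 / 68 | 65 / 62 |
| 960 (20% loss) | 77 / 75 | 73 / 70 | 66 / 63 | 60 / 56 |

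With 5% loss at 2:1 (1140 evaluable), power is 79.9 / 77.9%. With no loss, uncorrected power falls to 80% at a split of about 2.3:1, or 1200/3.3 ≈ 364 monotherapy patients.

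**Step 5: enrolment that would preserve 80% at 2:1.** N/(1 − loss), uncorrected / corrected: 10% loss, 1146/0.9 = 1274 and 1200/0.9 = 1334; 20% loss, 1146/0.8 = 1433 and 1200/0.8 = 1500. These show the size of the missing allowance; they are not a request to enrol more.

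**The case against.** The strongest reply is that the calculation is correct and that several harsher conclusions do not follow. Most of this stands.

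- *An arithmetic error.* A reader might infer one. There is none: 1200 and 0.682 both reproduce.
- *The split must be exactly 2:1, or 80% is an upper bound.* Neither is supported. Only a split more unequal than 2:1 costs power. At 1:1, power is 86/84% with no loss and still 82/80% with 10% lost. The documents do not show which way the split will go.
- *Every one of the 1200 is needed.* This holds only on the continuity-corrected formula. Without the correction, 1146 suffice.
- *A fifth to a third of patients will be missing.* Section 6.2 says that about "20 - 30 % of patients end their treatment with etanercept during the first year of treatment", and it is tempting to use this as the loss rate. It describes stopping treatment over a year, for lack of efficacy or side effects, whereas the power calculation concerns week 12. A patient who stops for lack of efficacy could be counted as not attaining the goal, and section 9.2 asks for clinical status to be documented where possible when participation ends. The figure bears mainly on the week 24 and week 52 parts of the RA end point.
- *Laboratory values will often be missing.* Table 1 schedules laboratory documentation at all five visits, and no missingness rate is given.

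It can also be said that section 8.5 promises an odds ratio with a 95% confidence interval, which would show imprecision directly, that section 8.9 already concedes selection bias and withdrawals, and that the questions listed in section 7 do not include the MTX contrast. These points limit the harm. They do not supply the missing allowance or a basis for the ratio, and section 8.5 still states sufficiency without conditions.

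**Conclusion.** The point holds as an unsecured planning assumption. The calculated evaluable number equals planned enrolment, the protocol itself anticipates withdrawals with unreplaced observations, and nothing in a non-interventional design fixes the 2:1 ratio. The design does not ensure the stated 80%; the documents do not show that it will fail to reach it.

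At 2:1, a 10% non-evaluable share puts power below 80% on either formula (78/76%). A 5% share leaves it at about 80% uncorrected and 78% corrected. A 3:1 split with no loss gives 75/73%, while a more even split improves on the plan. All of these figures take the 74% and 66% rates as given and compare the groups without covariate adjustment. The loss rates and splits are illustrative.

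**What to change.** In section 8.5:

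1. Say that 1200 is the evaluable number, and name the test behind it (the continuity-corrected two-proportion formula reproduces it).
2. State the expected share of RA patients who will lack the end point or fall outside the two regimens, and the basis for that share. Do not take it from the one-year discontinuation figure.
3. Give the basis for the 2:1 ratio.
4. Replace the flat 80% with a short table of power by evaluable number (1200, 1080, 960) and by split in both directions from the plan (1:1, 2:1, 3:1, 4:1), as in the working above.

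The cost is a rewording of one section. No extra patients and no change in data collection are needed. The downside is that the stated power looks less favourable under some of the scenarios shown.

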8.7. Data analysis

Absolute and relative adjusted frequencies are determined for categorical data. Numerical data are expressed using the sample statistics mean and standard deviation, as well as minimum, 1% percentile, 5% percentile, lower quartile, median, upper quartile, 95% percentile, 99% percentile and maximum.

The primary end point “proportion of patients attaining the desired treatment goal” will be analyzed using a logistic regression for the subgroups “RA patients with ETN+MTX” and “RA patients with ETN monotherapy”.

A detailed description of the statistical analysis of the data collected will be included in the SAP which will be dated, stored, and maintained by the sponsor. The SAP may modify the analyses described here. Every substantial amendment to the definition and analysis of the primary end point would take place in the form of a protocol amendment.

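### The RA comparison of ETN+MTX with ETN monotherapy makes no stated allowance for within-center correlation, so its 95% interval and 5% test may be miscalibrated

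*Combined protocol and SAP*

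**What the plan says.** Section 8.2.1 plans "about 2100 patients in 300 centers", of whom "about 1200 will have a diagnosis of RA and about 300 each will have a diagnosis of axSpA, PsA, and PsO". Section 8.5 bases the RA sample size on this: "Assuming that 74% of the patients under treatment with ETN + MTX and 66% of the patients under ETN monotherapy exhibit adequate response" at week 12 ("odds ratio of 0.682"). It arrives at 1200 patients for 80% power at a two-sided 5% level; "with a 2:1 ratio, this equals 800 patients under combined treatment and 400 patients under monotherapy".

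The method named in 8.5 is "A logistic regression quoting the odds ratio and the corresponding 95% confidence interval". Section 8.7 confines that model to RA: the primary end point "will be analyzed using a logistic regression for the subgroups" of RA patients on ETN+MTX and on ETN monotherapy.

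Neither section mentions a center effect, a cluster-robust variance, an ICC or a design effect. The only method for correlated data is a GEE in 8.5. It is an optional sensitivity analysis, its description suggests repeated visits within a patient, and no cluster unit is given. The limitations in 8.9 cover selection bias and early withdrawal, but not clustering. Sections 8.3 and 8.7 leave the details to a separate SAP, whose text is not in the document reviewed.

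**The concern.** A logistic regression without a center-level variance treats each patient as an independent observation. Two features of this study make that doubtful.

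- **Outcome.** The RA goal in Table 2 is a DAS28 threshold, and joints are examined in the treating center at every visit (Table 1). Section 6.2 adds that continuing treatment rests on the prescribing physician's judgment. Patients of one center share raters and treatment habits.
- **Regimen.** The study is non-interventional, so the physician and not the study decides on MTX. A preference for or against the combination may be a habit of the center.

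If both cluster by center, the model-based standard error of the odds ratio is too small, the 95% interval covers less than 95%, and the 5% test rejects too often. If the regimen is balanced within centers, the error runs the other way. This odds ratio is the study's only powered comparison.

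**Working it through.** **Inputs from the protocol.** 300 centers (8.2.1); 1200 RA patients (8.2.1, 8.5); 74% and 66% response, 800 and 400 patients, two-sided 5%, 80% power (8.5).

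**Assumptions.** ICC of the outcome 0.02 to 0.10, because no value is given. Mean RA cluster size m = 1200/300 = 4, which requires all 300 centers to enrol RA.

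**Step 1: reproduce the plan's figures.**

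Odds ratio = (0.66/0.34)/(0.74/0.26) = 0.682, as stated.

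Two-proportion formula for the monotherapy group, with r = 2, difference d = 0.08 and pooled rate (0.66 + 2×0.74)/3 = 0.7133:

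- n′ = [1.960×√(1.5×0.7133×0.2867) + 0.8416×√(0.66×0.34 + 0.74×0.26/2)]² / 0.08² = (1.0855 + 0.4765)² / 0.0064 ≈ 381.2
- With continuity correction: n = (n′/4)×[1 + √(1 + 2(r+1)/(n′·r·d))]² = (381.2/4)×[1 + √1.0984]² ≈ 399.8, so 400
- Total = 3×400 = 1200, an exact match.

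Without the continuity correction the total is 1146, and the power with 400 and 800 patients is 81.8%. Both forms assume independent patients, so 1200 contains no clustering allowance.

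**Step 2: upper bound, each center using one regimen.** Design effect DE = 1 + (m − 1)×ICC. Naive SE shortfall = 1 − 1/√DE. Test size = 2×[1 − Φ(1.96/√DE)]. Power uses 400/DE and 800/DE patients, without continuity correction.

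| ICC | DE | Naive SE too small by | Coverage of 95% CI | Size of 5% test | Power (81.8% if independent) |
|---|---|---|---|---|---|
| 0.02 | 1.06 | 2.9% | 94.3% | 5.7% | 79.6% |
| 0.05 | 1.15 | 6.7% | 93.2% | 6.8% | 76.4% |
| 0.10 | 1.30 | 12.3% | 91.4% | 8.6% | 71.3% |

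If RA were enrolled in only 200 centers (m = 6), DE would be 1.10 to 1.50 and the test size 6.2 to 11.0%. Unequal center sizes would also raise these values.

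**Step 3: both regimens used within centers.** Approximately, DE = 1 + (m − 1)×ICC×ICC of treatment. At an outcome ICC of 0.10 and a treatment ICC of 0.3, DE = 1 + 3×0.10×0.3 = 1.09 and the size is about 6.0%. At a treatment ICC of 0.5, DE = 1.15 and the size is 6.8%.

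A simulation of 300 centers with 4 RA patients each (4000 runs, common rate 0.71, outcome ICC 0.05 to 0.20, so extending above the range in step 2) gave these rejection rates for the naive test:

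- no center preference: 4.6 to 5.3%
- moderate preference (treatment ICC 0.3): 5.5 to 6.5%
- strong preference (treatment ICC 0.5): 6.1 to 9.0%
- one regimen per center: 6.7 to 11.2%

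The Monte Carlo standard error near 5% is √(0.05×0.95/4000) ≈ 0.3 percentage points.

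**Step 4: the same 1:2 mix in every center.** Simulated with 6 patients in each of 200 centers, the naive test rejected in 4.1%, 3.6% and 2.7% of runs at ICC 0.05, 0.10 and 0.20. This agrees with a variance factor of 1 − ICC, which gives 4.4%, 3.9% and 2.8%. The test is then conservative.

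**The case against.** The strongest reply is that the protocol is silent rather than wrong. It lists no covariates at all and hands detail to a SAP that may modify the analyses and could still add a center adjustment. That is fair, and it is why the point concerns what is unspecified. It does not remove the point: the method that is stated has no center term, and nothing in the protocol asks the SAP to add one.

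The second reply is that the effect is small and may not inflate anything. This also stands. At 4 patients per center the bound is modest, and inflation requires regimen choice to cluster by center, on which the documents give no data.

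A reader might also infer more than the documents support:

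- **That about 2100 patients, 7 per center, enter the model as independent.** With m = 7 and ICC 0.02 to 0.10 the design effect would be 1.12 to 1.60, with coverage down to 88% and a test size up to 12%. But 8.7 restricts the regression to RA, and no planned model pools all 2100.
- **That the week-12 and week-24 goal rates have intervals that are too narrow.** Section 8.7 plans frequencies for categorical data. The only interval named is for the RA odds ratio. The concern applies to goal-rate intervals only if they are reported.
- **That each 300-patient indication is worth only 188 to 268 independent patients** (300/1.60 to 300/1.12). This needs 7 such patients per center, so all 300 in about 43 centers, which the protocol does not say. Spread over 300 centers, the mean is 1 per center and the design effect about 1.
- **That the RA interval and test are certainly too optimistic.** Steps 3 and 4 show that they may be about right or conservative.

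**Conclusion.** The point holds for the RA comparison of about 1200 patients. The plan states a logistic regression with no allowance for within-center correlation, and the sample size contains none. The naive interval is miscalibrated in one direction or the other unless outcomes are uncorrelated within center or regimen is unrelated to center.

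The bound in step 2 rests on an assumed ICC of 0.02 to 0.10, a mean of 4 RA patients per center and one regimen per center: at most 3 to 12% on the standard error and a test size of about 6 to 9%. More mixing of regimens within centers moves the size toward 5% and, with an equal mix everywhere, below it. The point is worth correcting because the remedy is cheap and handles either direction. It is not evidence that the planned result would be wrong.

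**What to change.** In 8.5, 8.7 and the SAP:

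1. State that the RA logistic model uses center as the cluster. Either fit a GEE with exchangeable working correlation and robust standard errors, or keep the same logistic model and attach center-cluster-robust standard errors. Both keep a population-averaged odds ratio, the scale on which 8.5 states its assumption. The second leaves the point estimate unchanged.
2. Name the cluster unit of the GEE already listed in 8.5, so that repeated visits and shared centers are not confused.
3. Use the same center-level variance for any goal-rate interval or cross-indication contrast that is reported. Comparing rates across indications is part of the primary goal in section 7.
4. Report the observed ICC and the distribution of RA patients and regimens over centers.

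**Cost.** Slightly more analysis work and intervals that may be slightly wider. No new data are needed beyond the center of each patient. Section 8.7 requires a protocol amendment for a substantial change to the primary analysis, so an amendment may be needed. It would best be settled before the interim analyses planned in 11.1.
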